**SOC Cooled Radiofrequency ablation (C-RFA) of Residual Limb Neuroma Procedure:**

*C-RFA:*

Our RFA procedures will be performed similar to methods described by Zhang et. al and Kim et. al with modification accounting for appropriate C-RFA technique. This technique is currently standard clinical practice at University of Utah outpatient clinic sites. During the C-RFA procedure, the participant will be positioned prone. The participant's skin will be prepared with chloroprep. An ultrasound probe will be placed on the participants' residual limb at a transverse angle in order to view the nerve and associated neuroma in long-axis. The probe will be advanced to the site of the stump neuroma. An 18-gauge C-RFA electrode with a 4mm active tip (Coolief® Cooled Radiofrequency Kit, Avanos Health Inc, Alpharetta, GA) will be placed adjacent to the neuroma. This needle will be connected via wire to a cooled radiofrequency generator. Motor testing will be performed (2.0 V, 2Hz). Sensory testing will be performed (1.0 V, 50Hz) to reproduce or exacerbate the RLP and / or PLP. At the site of the neuroma, 2 mL of local anesthetic will be injected through the needle (without triamcinolone as used per Zhang study). When the local anesthetic demonstrates pain relief, the needle will be placed into the nerve. C-RFA lesions will be created by using the typical C-RFA protocol with lesions performed for 165 seconds, with the RFA generator temperature set to 60°C (intralesional temperature >80 degrees). Once the procedure is completed, the needle will be removed. Following ablation, 0.5 mL of 0.5% bupivacaine will be injected at the site of the ablated neuroma to provide post procedure analgesia. No corticosteroids will be injected.

Following the Standard Treatment Procedure visit, routine scheduled follow-up will occur at 1 month (+/- 1 week), 3 months (+/- 2 weeks), 6 months (+/- 2 weeks), and 12 months (+/- 2 weeks) at which times all follow-up measures will be obtained. These questions will be administered over the phone or be sent to you using a secure REDCap survey by email. If received by email it will be in the form of two e-mail links in which you will again be asked questions regarding your pain level, changes in activity limitations, symptoms, emotions and

overall quality of life related to your painful condition and to record current use of opioid and non-opioid analgesic use. This part of the survey should take 10 minutes.

This study is intended to monitor outcomes for 12 months following C-RFA of residual limb neuroma.

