## **Procedures:**

Screening Visit: As participants are identified by the PI or CO-I's as being possible candidates for this study they will be invited to participate. Main inclusion requirement, as listed in inclusion criteria, is that the patient is being scheduled for residual limb neuroma radiofrequency ablation (RFA) procedure as standard of care. If patient states interest in the study and wishes to discuss in more detail a research coordinator will discuss at time of appointment or call and answer any questions at a time convenient to the patient. If patient is interested, and does meet inclusion/exclusion criteria, and does not have time to do the baseline questions at time of appointment a qualified research staff member will call the patient to complete by phone. It is anticipated that most subjects in this study will be identified mainly through the regular flow of the University of Utah clinics. The informed Consent process will occur either at the time the subject is in clinic or the participant may elect to complete the process at a later time. Eligibility is determined by the inclusion and exclusion criteria. Qualifying volunteers will be asked to provide both written and verbal informed consent once a standard of care treatment plan has been agreed upon by the patient and treating physician.

Baseline: Participants who meet inclusion and exclusion criteria will be enrolled into the study after consenting to participate and before receiving residual limb neuroma RFA. This procedure is considered standard of care and are typically based on physician preference. Baseline data will be collected within 2 weeks prior to the scheduled procedure, this will include information from their examination and baseline questionnaires which include the following:

An electronic data collection system (REDCap via computer) will be used to record all pre-procedure and follow-up data as listed above (See attached PDF for baseline survey)

1. Age (years).
2. Sex
3. Height (cm).
4. Weight (Kg).
5. Duration of pain (weeks).
6. Date of amputation
7. Etiology of amputation
8. Level of amputation
9. Radiologic diagnosis based on ultrasound of residual limb.
10. Patient-Reported Outcomes Measurement Information System (PROMIS) 10
11. Analgesic medication log: dose and frequency of each medication
12. Brief Pain Inventory (BPI) with modification to include numerical rating scale (NRS) score (worst, least, average, current).

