13. Groningen Activity Restriction Scale (GARS)
14. Pinprick Sensory Threshold (Von Frey Hair testing at the neuroma site)
15. Pressure Pain Threshold (algometer testing at the neuroma site)

Additional questions for post procedure survey

16. Patient Global Impression of Change (PGIC)

Patient satisfaction score (five-point Likert scale: 1, very dissatisfied; 2, dissatisfied; 3, neither satisfied nor dissatisfied; 4, satisfied; and 5, very satisfied)

Immediately after ablation the following will be obtained:

17. Post-injection Numeric Rating Scale (NRS) pain score

18. Adverse events, if they occurred

Questionnaires will be administered and collected from the participant through the University of Utah approved survey system of REDCap.

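### Must the plan change because von Frey and algometer tests are on the data list while follow-up is described only as phone or e-mailed survey?

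*Combined protocol and SAP*

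**What the plan says.** Procedures introduces the data list as baseline information: "Baseline data will be collected within 2 weeks prior to the scheduled procedure". It adds that this information comes from the participant's examination as well as from baseline questionnaires. The next sentence says REDCap "will be used to record all pre-procedure and follow-up data as listed above". The list then runs from demographics and amputation history (items 1 to 9) through PROMIS-10, an analgesic log, the BPI with NRS, and GARS (items 10 to 13). It ends with two device-based tests: "Pinprick Sensory Threshold (Von Frey Hair testing at the neuroma site" (item 14) and "Pressure Pain Threshold (algometer testing at the neuroma site" (item 15).

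Under "Additional questions for post procedure survey" the protocol adds PGIC and a satisfaction score. NRS and adverse events immediately after ablation follow as items 17 and 18.

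The C-RFA procedure section sets routine follow-up at 1, 3, 6 and 12 months, "at which times all follow-up measures will be obtained", without listing those measures. On mode it says "These questions will be administered over the phone or be sent to you using a secure REDCap survey by email". The survey content it then describes is pain, activity limitation, symptoms, emotions, quality of life and analgesic use, in about 10 minutes.

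**The concern.** A filament or an algometer has to be applied to the limb by an examiner. If the whole list is meant to be collected again at each follow-up time, the two tests are scheduled with no described occasion on which they can be done. Baseline looks open too, because for a patient short of time at the appointment "a qualified research staff member will call the patient to complete by phone".

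The worry would be a change-from-baseline result for the thresholds that either does not exist or comes only from participants who happened to attend clinic. In an uncontrolled single-arm pilot, these are the only examiner-measured items among the outcome-type measures. A selective subset could then be mistaken for objective support of the self-reported results.

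**Working it through.** The plan gives no figure to reproduce, and no sample-size or power input is involved. The check is to read the relevant sections against each other.

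**1. Does the list have to be repeated in full?** No. It is headed as baseline data, and items 1 to 9 include age, sex, date of amputation and etiology. The sentence covering pre-procedure and follow-up data therefore cannot mean that every item recurs. It also points to a list above itself, while the only list comes below, so it is weak evidence of scope. PGIC and satisfaction are added as survey questions, which says nothing about physical tests. Repetition of items 14 and 15 is implied at most.

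**2. Does the mode sentence make all follow-up remote?** No. Its subject is the questions. The described survey content contains no threshold test, which fits a reading in which the tests were never part of follow-up. Routine follow-up might include clinic attendance, but the protocol does not say so. The section on research-only procedures lists surveys alone, which is consistent with the tests belonging to the ordinary examination.

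**3. Is there a place for the tests at baseline?** Yes. Baseline data expressly include information from the examination, inside a 2-week window. The telephone allowance concerns the baseline questions only.

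**4. Which results depend on follow-up thresholds?** None that is named. The objective is change in pain, physical function and health-related quality of life. The Data Analysis Plan names pain relief, PGIC and MQS III. Statistical analysis promises means, standard deviations, proportions and 95% confidence intervals, and refers to other outcomes only in general terms.

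**5. What happens under each reading?**

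| Reading of items 14 and 15 | Thresholds | Pain, function, quality of life |
|---|---|---|
| Baseline only | Baseline description, no change reported | Unaffected |
| Repeated for all at routine clinic visits | Change available | Unaffected |
| Repetition intended, no visit in clinic | No follow-up values | Unaffected |
| Repeated only for some | Change on a subset, readable only with the number tested | Unaffected |

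**6. Count.** Items 10 to 16 are 7 measures, and satisfaction makes 7 + 1 = 8. Two need a device, so 8 − 2 = 6 can be collected remotely, and 2/8 = 25%. Counting items 17 and 18 as well gives 2/10 = 20%. The share depends on what is called an outcome and does not measure harm.

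**The case for a change.** The best argument for a change is that age and sex are obviously baseline-only, whereas a sensory threshold at the treated site is not. Items 14 and 15 sit next to PROMIS-10, BPI and GARS, which are plainly meant to be repeated, so staff cannot tell which group the tests belong to. The Data Analysis Plan also applies a responder rule of more than 30% improvement to secondary measures that lack an MCIC. Its list of secondary outcomes is not closed, so the thresholds could be drawn in, and that rule needs a post-baseline value. The stated sample size is 10 or 20 depending on the line read, and either is small enough for a partly tested subset to be a handful of people.

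Part of this stands: the protocol does not say whether the tests are repeated, and no described procedure yields a follow-up threshold. The step from there to damage does not stand. The plan never classes the thresholds as secondary outcomes. If they were, a responder rule without follow-up values would produce no result, not a wrong one. Selective testing in clinic is conjecture, and neither its extent nor its direction can be taken from the documents.

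The available remedies gain little. Declaring the tests baseline-only settles wording that an analyst would settle the same way. Repeating them at a follow-up visit depends on clinic attendance that the protocol does not establish. Without it, extra visits would be needed for measures outside the stated objective.

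**Conclusion.** No change to the plan is needed. The inconsistency is real as a matter of drafting, but it is missing detail that those running and analysing the study can fill sensibly: read items 14 and 15 as part of the baseline examination and report no threshold change unless follow-up values exist. Two listed tests are affected and no named objective or analysis is. The effect on the pain, function and quality-of-life results is nil under every reading considered.

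This rests on two assumptions. First, the thresholds are not intended as a main outcome, which fits their absence from the objective and the analysis sections. Second, the baseline survey that the protocol mentions as an attachment, which was not available, does not give them a larger role. If a report did present threshold change, the number tested out of the number treated would have to stand beside it; that is ordinary reporting practice and needs no amendment.

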**Procedures performed for research purposes only:**

1. survey/questionnaire

## **Statistical Methods, Data Analysis and Interpretation**

---

### **Data Analysis Plan**

A categorical responder analysis will also be performed using >50% pain relief in PLP and RLP, as well as the minimally clinically important change (MCIC) for secondary outcome measures for which an MCIC has been defined, and >30% improvement for secondary outcome measures for which an MCIC has not yet been defined.

While there is no standard residual limb pain outcome recommendation, the NIH's recommendation on pain interventions was applied to this study. These secondary outcomes include PGIC score less than 3 (indicating "improved" or "very much improved"), a 6.8 or greater point reduction on the MQS III score (equivalent to approximately 10 daily morphine equivalents).

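### The plan calls for >50% relief in both phantom and residual limb pain, but no listed pain rating is labelled by pain type

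*Combined protocol and SAP*

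**What the plan says.** The Data Analysis Plan sets the responder criterion: "A categorical responder analysis will also be performed using >50% pain relief in PLP and RLP". The Statistical analysis section adds that categorical data will be given as proportions with 95% confidence intervals.

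The pain measures are listed under Procedures:

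- Baseline: "Brief Pain Inventory (BPI) with modification to include numerical rating scale (NRS) score (worst, least, average, current").
- Sensory tests: "Pinprick Sensory Threshold (Von Frey Hair testing at the neuroma site") and "Pressure Pain Threshold (algometer testing at the neuroma site").
- Immediately after ablation: "Post-injection Numeric Rating Scale (NRS) pain score".
- Follow-up at 1, 3, 6 and 12 months, described in the section on the C-RFA procedure: participants are "asked questions regarding your pain level". On the mode of collection: "These questions will be administered over the phone", or by an emailed REDCap link.

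Item wording is left to an attachment: "See attached PDF for baseline survey". That attachment was not among the documents reviewed.

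The Introduction groups RLP and PLP under one umbrella term, post-amputation pain. It also describes them as different in features and cause, often present together, and hard for patients to tell apart. The Objectives section names neuroma-associated residual limb pain only.

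**The concern.** The endpoint is worded for two pains, while the listed ratings ask about pain without saying which. If the survey matches the list, one score has to stand for both. Such a score cannot show whether the pain named in the objective (RLP) improved, whether PLP improved, or both.

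The loss is permanent. An overall rating given at the 3-month visit cannot later be divided into its two parts. The Introduction says that this pilot is to inform a powered randomized trial, and that trial will need a relief rate for its target pain. By the protocol's own account the two pains commonly co-occur, so a mixed score is a realistic prospect.

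**Working it through.** **1. Listed measures set against the endpoint.** The endpoint needs a before-and-after rating of RLP and of PLP.

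| Listed measure | Rates pain intensity? | Labelled RLP or PLP? |
|---|---|---|
| Modified BPI with NRS worst, least, average, current | Yes | No |
| NRS immediately after ablation | Yes | No |
| Pain level at follow-up | Yes | No |
| Von Frey test at the neuroma site | No, a sensory threshold | Tied to the residual limb; says nothing on phantom pain |
| Algometer test at the neuroma site | No, a pressure threshold | Same |

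The sensory stimulation during the procedure mentions both pains, but it is a procedural step and not a recorded outcome. No row supplies a relief figure for either pain type.

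**2. Can one unlabelled score identify response by pain type?** The documents do not say how a patient with both pains would arrive at one number. Two simple rules are assumed here; neither is in the documents. Relief = (baseline − follow-up) / baseline.

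*Assumption A: the score is the worse of the two pains.* An overall change from 8 to 3 is 5/8 = 62.5%, a responder. It fits each of these:

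- RLP 8 to 3 (62.5%), PLP 3 to 3 (0%): response in RLP only.
- RLP 3 to 3 (0%), PLP 8 to 3 (62.5%): response in PLP only.
- RLP 8 to 3 (62.5%), PLP 6 to 2 (4/6 = 66.7%): response in both.

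*Assumption B: the score is the mean of the two pains.* An overall change from 7 to 3 is 4/7 = 57.1%, a responder. It fits each of these:

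- RLP 8 to 5 (3/8 = 37.5%), PLP 6 to 1 (5/6 = 83.3%): response in PLP only.
- RLP 8 to 1 (7/8 = 87.5%), PLP 6 to 5 (1/6 = 16.7%): response in RLP only.

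Under either rule the single score does not determine which pain responded.

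**3. Can the size of the misclassification be stated?** Take one patient, RLP 8 to 5 and PLP 6 to 1, under both rules:

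- Mean: (8 + 6)/2 = 7 to (5 + 1)/2 = 3, relief 57.1%. Classed as a responder although RLP relief is 37.5%.
- Worse: 8 to 5, relief 37.5%. Classed as a non-responder, which agrees with RLP.

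Now take RLP 8 to 2 (6/8 = 75%) with PLP constant at 5:

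- Mean: 6.5 to 3.5, relief 3/6.5 = 46.2%. Classed as a non-responder although RLP responded. A diagnostic block taking RLP to 0 would give 6.5 to 2.5, relief 4/6.5 = 61.5%, so this patient could pass the >50% block criterion.
- Worse: 8 to 5, relief 37.5%. The same block gives 8 to 5, also 37.5%, so this patient would fail the block criterion if it were scored on that rating and would not be enrolled.

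The classification, and even eligibility, turns on the assumed rule. No magnitude follows from the documents.

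**The case against.** **The survey has not been seen.** The Procedures section names instruments, not item wording, and says that the BPI has been modified. The follow-up text addresses the participant and is not an endpoint specification. A reader might infer that the trial certainly cannot produce the two rates. The documents do not support that; they show only that no listed rating is labelled. This objection stands, and the point is conditional on it. Even so, the plan would need to name the items that feed the endpoint.

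**The phrase may mean combined pain.** Given the umbrella term in the Introduction, one rating could serve. This reading is possible, but the plan does not state it and the same section stresses how the two pains differ. If it was intended, the endpoint needs rewording.

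**Eligibility narrows the problem.** Relief above 50% from a neuroma block, with imaging that fits the symptoms, selects for neuroma-driven pain. That makes a mixed score less likely to mislead, but it does not exclude PLP or label the score.

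**Participants without PLP.** A reader might infer that people with no phantom pain will certainly be enrolled. Inclusion criterion 3 is blank in the available text, so a requirement on baseline pain type cannot be ruled out.

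**Split items may promise more than patients can deliver.** The Introduction itself says that patients have trouble separating the two. This stands as a limit on the fix. An unlabelled item does not remove the confusion; it only hides it.

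**This is a small descriptive pilot.** True, and no hypothesis test depends on the rate. A reported proportion still needs a defined numerator and denominator.

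**Conclusion.** The point holds in conditional form. On the listed measures, relief in RLP and relief in PLP cannot be derived separately, and the information cannot be recovered after the visit. Nor could one unlabelled score show whether the target pain or phantom pain changed. Two things would remove the problem: split items in the attached survey, or an intended meaning of combined post-amputation pain. Neither can be confirmed from the documents.

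No size is claimed. A reader might take the 57% against 37.5% example as evidence that responders will be miscounted in a known direction. It is not: the two figures describe the same patient under two assumed reporting rules, and the documents give neither rule.

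The plan also leaves open which of the four NRS scores and which visit define a responder. That is missing detail, and choosing one main item and visit is a design preference; this conclusion does not rest on it. The point should be fixed because the remedy changes what is collected and so must be in place before the visits occur.

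**What to change.** At baseline and at 1, 3, 6 and 12 months, add one 0-10 NRS for pain in the part of the limb that remains (RLP) and one for pain felt in the part that is missing (PLP). Give each a short definition that works by phone and in REDCap. If the survey already has split items, name them in the plan instead.

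Report the RLP and PLP responder rates separately, each with its 95% CI. Calculate the PLP rate only in participants with baseline PLP above 0, since percentage relief is undefined at 0, and show that n beside the number enrolled. If combined pain was intended, restate the endpoint as overall post-amputation pain; no new items are then needed for it.

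The cost is two items at five time points (2 × 5 = 10 extra answers per participant) and a short paragraph in the plan. Some confusion between the two pains will remain despite the definitions. The PLP rate will have a wider interval if fewer participants contribute. At an observed 50%, the exact (Clopper-Pearson) 95% CI is 27-73% for 10 of 20, 19-81% for 5 of 10, and 16-84% for 4 of 8. The first two sizes are the figures in the Sample Size section (20 at Utah, 10 for all centers), whose conflict is a separate matter; 8 is an assumed smaller PLP subgroup.

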No outcome literature on the effectiveness of C-RFA technology has been published. C-RFA is similar in mechanism to conventional RFA: a thermal lesion is created by applying radiofrequency energy through an electrode placed at a target structure. In C-RFA, a constant flow of ambient water is circulated through the electrode via a peristaltic pump, maintaining a lowered tissue temperature by creating a heat sink. By removing heat from tissues immediately adjacent to the electrode tip, a lower lesioning temperature is maintained, resulting in less tissue charring adjacent to the electrode, less tissue impedance and more efficient heating of target tissue. The volume of tissue heated, and the resultant thermal lesion size is substantially larger with C-RFA, conferring an advantage over conventional RFA. Further, given the spherical geometry and forward projection the C-RFA lesions beyond the distal end of the electrode, the RFA probe can be positioned at a range of possible angles and still capture the target neural structure, whereas more fastidious, parallel positioning is required with conventional RFA. These technical advantages increase the probability of successful denervation of neural pain generators that have variability in anatomic location. Additionally, a longer lesion of the RLP-generating nerve may be more reliably achieved with C-RFA compared to conventional RFA.

As such, the present study aims to define the attributable effect of cooled RFA on pain, physical function, and health-related quality of life in patients with post-amputation neuroma-associated residual limb pain. This prospective single-arm pilot study is intended to inform a future properly powered randomized controlled trial.

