### Inclusion Criteria:

### Inclusion Criteria:

1. Age greater than 18 years of age at day of enrollment.
2. Clinical diagnosis lower extremity amputation performed more than 1 year since study enrollment.
3. .
4. Pain duration of more than 6 months despite a trial of conservative therapy (medications, physical therapy) for 2 months.
5. Ultrasound and / or MRI imaging pathology consistent with clinical symptoms and signs.
6. Greater than 50% pain relief with a diagnostic neuroma block

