### **Exclusion Criteria:**

#### Exclusion criteria:

1. Refusal or inability to participate, provide consent, or provide follow-up information for the 12-month duration of the study.
2. Contraindications to diagnostic block or treatment ablation (active infection, bleeding disorders, and pregnancy or breastfeeding, active immunosuppression, participation in another phantom or residual limb pain trial within the last 30 days)
3. Non-neurogenic source of residual or phantom limb pain.
4. Active moderate to severe lumbar radiculopathy.
5. Any injection in the residual limb within the last 30 days.
6. Severe uncontrolled medical condition as determined by treating physician.
7. Severe psychological illness.
8. History of Inflammatory arthritis.
9. Malignancy within past 5 years except basal cell or squamous cell skin cancer.
10. Current opioid use exceeding 50 morphine milligram equivalents per day.
11. A history of alcohol or drug abuse within past 5 years.
12. Use of any investigational drug within past 30 days.
13. Pending litigation involving participant's residual limb pain.
14. Incarceration

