### Statistical analysis

Means and standard deviations of participant demographic data, as well as pain, functional, and other outcome data will be calculated. Proportions and 95% confidence intervals will be calculated for categorical data.

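### Pain response is defined without regard to analgesic use, and the planned summaries cannot show whether pain responders were the participants whose analgesics rose

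*Combined protocol and SAP*

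**What the plan says.** The Data Analysis Plan section of the combined protocol and SAP defines pain response by relief alone: "A categorical responder analysis will also be performed using >50% pain relief in PLP and RLP". Medication enters only as a separate secondary outcome: "a 6.8 or greater point reduction on the MQS III score (equivalent to approximately 10 daily morphine equivalents". That rule counts falls; no rule addresses a rise.

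The Statistical analysis section then plans two kinds of summary: "Means and standard deviations of participant demographic data, as well as pain, functional, and other outcome data will be calculated", and "Proportions and 95% confidence intervals will be calculated for categorical data". Neither section cross-classifies pain response with medication change, requires stable analgesics, or says how relief with an analgesic increase is counted.

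The Introduction sets the aim: "the present study aims to define the attributable effect of cooled RFA on pain", along with physical function and quality of life. It also sets the design: "This prospective single-arm pilot study is intended to inform a future properly powered randomized controlled trial".

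Analgesic use is collected. The baseline list under Procedures includes a medication log with dose and frequency. The C-RFA procedure section says all follow-up measures are obtained at 1, 3, 6 and 12 months, and that the follow-up survey records current opioid and non-opioid analgesic use.

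**The concern.** A participant who reports more than 50% relief while taking more analgesics than at baseline is a pain responder under this rule. With no control arm, the added medication is a competing explanation for that participant's relief, and the plan never reports how often the two occur together.

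The rule also errs the other way. Someone with 40% relief who has cut analgesics substantially is a pain non-responder, although the procedure may have helped.

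At stake is how the pain responder rate can be read when it informs the randomized trial. A reader could not tell relief at stable or lower analgesic use from relief with escalation, although the study intends to hold the data that would tell them apart.

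**Working it through.** The plan has no figure of its own to reproduce here: it gives no expected response rate, no frequency of analgesic increases and no baseline MQS III. All counts below are assumptions. The inputs taken from the document are the >50% rule, the 6.8-point threshold, and the Sample Size section's two figures, 20 at Utah and 10 for all centers. Those two conflict and must be reconciled, so both are used.

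**Step 1: can the planned summaries identify the joint event?** Take four participants with the same baseline MQS III (at least 10), two of them pain responders.

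| | MQS III change, responders | MQS III change, non-responders |
|---|---|---|
| Case A | +10, +10 | -10, -10 |
| Case B | -10, -10 | +10, +10 |

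In both cases:
- mean change = (10 + 10 - 10 - 10)/4 = 0
- SD of change = √(400/3) ≈ 11.5
- pain responders = 2/4 = 50%
- MQS III fall of 6.8 or more = 2/4 = 50%

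Every planned summary agrees. Yet the rate of relief without a rise of 6.8 or more is 0/4 in A and 2/4 in B. The SD signals that changes were large and offsetting, but not who rose.

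**Step 2: how far can the two rates differ?** With R pain responders and U increasers among n participants, the overlap lies between max(0, R + U - n) and min(R, U). Intervals are exact (Clopper-Pearson) 95%.

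- n = 20, R = 10, U = 5: the overlap is 0 to 5. The planned rate is 10/20 = 50% (27.2 to 72.8). Relief without a rise is between 5/20 = 25% (8.7 to 49.1) and 10/20 = 50%.
- n = 10, R = 5, U = 2: the overlap is 0 to 2. The planned rate is 5/10 = 50% (18.7 to 81.3). Relief without a rise is between 3/10 = 30% (6.7 to 65.2) and 5/10 = 50%.

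**Step 3: what does one responder with a rise do?** Each moves the companion rate by 1/n.

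- n = 20: one gives 9/20 = 45% (23.1 to 68.5); two give 8/20 = 40% (19.1 to 63.9).
- n = 10: one gives 4/10 = 40% (12.2 to 73.8).
- If no responder had a rise, nothing changes.

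**Step 4: the denominator.** If the pain-only rate uses everyone with pain data and the companion rate only those with both measures, the companion rate can come out higher: 10/20 = 50% against, say, 9/16 = 56%. That would mix missing medication data with the quantity of interest. On a common denominator the companion rate can only equal or fall below the pain-only rate, because its numerator is a subset.

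**The case against.** The strongest reply is that this is a descriptive pilot with no hypothesis test, and reporting pain and medication as separate outcomes is a legitimate choice. The difficulty of attribution comes from having no control arm, which no cross-tabulation repairs, and shifts of one or two responders are small against intervals this wide. All of that stands, and it keeps the point minor. It does not remove the gap: the joint event bears directly on the stated aim and goes unreported although the data are planned.

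Three stronger readings are tempting and are not supported.

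- **That the pain rate overstates the effect.** The rule can also miss participants who reduced analgesics with 50% relief or less. The documents give neither frequency, so the net direction is unknown.
- **That the planned summaries conceal analgesic change altogether.** If MQS III is summarised among the other outcomes, its mean could show net escalation and its SD, for change scores, could show spread. Only the link to pain response is lost.
- **That many participants cannot meet the 6.8-point rule.** Entry requires a past treatment trial ("Pain duration of more than 6 months despite a trial of conservative therapy (medications, physical therapy) for 2 months") and excludes only high opioid use ("Current opioid use exceeding 50 morphine milligram equivalents per day"), so a low baseline score appears possible. But the documents give no MQS III scoring, minimum or baseline distribution, the log covers non-opioids as well, and one inclusion item is blank in the available text. This supports a descriptive count and no more.

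The data claim also has a limit. The follow-up survey text mentions current analgesic use without dose or frequency, and that MQS III is scored from the log is an inference. Still, the plan already commits to an MQS III change rule, which needs such data at both times.

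**Conclusion.** The point holds as a minor, cheap improvement. As defined, the pain responder rate can include relief that accompanied added analgesics, and separate means, SDs and proportions cannot show whether responders were the participants whose use rose.

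Its size cannot be determined from the documents and could be zero. In the illustrations, the rate of relief without a rise could lie anywhere from 25% to 50% at n = 20, or 30% to 50% at n = 10. These ranges rest wholly on the assumed counts of responders and increasers. The conclusion that the joint event is unreported needs none of those assumptions; it follows from the text and from Step 1.

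**What to change.** Keep the planned pain-only rate. Add to the Data Analysis Plan, for 1, 3, 6 and 12 months, among participants with both pain and MQS III data at baseline and that visit:

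- a cross-tabulation of pain response by MQS III change: fall of 6.8 or more, change of less than 6.8 in either direction, rise of 6.8 or more;
- from those same participants, with exact 95% intervals, the pain-only rate and the rate of >50% relief without an MQS III rise of 6.8 or more;
- a sensitivity version of the companion rate that excludes any rise;
- the number missing MQS III and, as a simple descriptive count, the number with baseline MQS III below 6.8.

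Using 6.8 in both directions applies the plan's own threshold and avoids disqualifying a responder for a trivial rise; the sensitivity version shows whether that choice matters.

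The cost is a few sentences and a few extra figures per visit, with no new instrument. The intervals will be wide at 10 to 20 participants. The companion rate may understate the effect, since a rise in analgesics need not have caused the relief, so it should sit beside the planned rate and not replace it.
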